***Sample Size and Statistical Analysis:***

The FILM trial is a non-inferiority study comparing lymph node detection rates between Blue dye and PINPOINT. A sample size of approximately 150 evaluable subjects (to identify 525 LNs) is required to show the LN detection rate for PINPOINT is non-inferior to that with Blue dye with 80% power and a 5% 2-sided significance level with a 5% non-inferiority margin.

Both a modified Intent-to-Treat (mITT) and Per-Protocol (PP) analysis population will be utilized for the primary analysis. Analysis of the primary objective will be conducted using a 2-sided 95% confidence interval for the difference in proportions. A non-inferiority test will be conducted using the PP and the mITT analysis populations. If and only if non-inferiority is claimed, a superiority test will be conducted using the mITT analysis population. As a supporting analysis of the primary outcome, the analysis will also be repeated using the as-treated (AT) population. The secondary objectives will be tested using a two-sided 5% significance level with a step-down multiplicity adjustment.

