#### 10.4 Sample Size Considerations

The clinical literature provides an estimate of the expected effectiveness of LN mapping with ICG and Blue Dye. 12 studies using ICG for the purposes of LN mapping have been published (Table 1). Detection rates for LN mapping with ICG and Blue dye are reported to occur in a wide range (33-100% for ICG and 40-80% for Blue dye). A number of factors play a role in the identification of LN including tumor size, familiarity with LN mapping technique (learning curve) and obesity.

A weighted average of published LN detection rates for Blue dye and ICG (i.e., PINPOINT) in gynecological cancer suggests unilateral detection rates of 91% for ICG and 80% for Blue dye. However, we assumed LN detection rates in gynecological cancer of 84% and 80% using ICG and Blue dye, respectively. We used a lower LN detection rate of 84% for ICG and a LN detection rate at the upper end of the range for Blue dye as a conservative approach to the sample size calculation. We also assumed a non-inferiority margin of 5%.

The power calculation was performed for a 2-level hierarchical model in which nodes are nested within subject. Power was calculated as a function of the effective sample size (ESS), which is a function of the total number of nodes excised, the number of nodes within subjects (clusters), and the intra-cluster correlation (ICC). Specifically,  $ESS = n / VIF$ , where  $n$  is the total number of nodes excised across all patients, and VIF is the variance inflation factor, calculated as

$VIF = 1 + (m - 1) \times ICC$ , where  $m$  is the number of nodes per subject. Because we expect to excise 3 to 4 nodes per subject, with 150 subjects we expect to excise  $3.5 \times 150 = 525$  nodes. With 3.5 nodes per subject on average and an ICC at most 0.125 we will have VIF at most  $1 + (2 \times 3.5 - 1) \times 0.125 = 1.75$  and an ESS at least  $525 / 1.75 = 300$  nodes. Note that here  $m$  is twice the number of expected nodes per subject, since nodes will be identified using 2 different methods within the same subject. We expect the ICC to be at most 0.125 based on our estimate of the ICC = 0.07 from Crane et al..

With an ESS of at least 300 Ns we will have at least 82% power to reject  $H_{01}$  above and claim non-inferiority of PINPOINT with respect to Blue dye. This sample size calculation was

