## 10.6 Secondary Objectives

The planned secondary outcomes are intended to support product labelling. We will use the step-down method described by Benjamini and Liu to control the false discovery rate at 0.05 (2-sided) while testing our secondary objectives.

The first secondary outcome is the ability of PINPOINT and Blue dye to detect at least one lymph node in a subject.

Let  $q_t$  and  $q_c$  represent the proportion of subjects with at least one lymph node identified (according to [section 8.3.1.5](#) and confirmed by histology) with PINPOINT and Blue dye respectively, divided by the total number of subjects where mapping was attempted. That is, the numerator for  $q_t$  is the number of subjects with at least 1 node identified with PINPOINT (classifications 1, 3, 5, 7) and confirmed as lymphoid tissue, and the numerator for  $q_c$  is the number of subjects with at least 1 node identified with Blue dye (classifications 2, 3, 6, 7) and confirmed as lymphoid tissue. The denominator of both  $q_t$  and  $q_c$  is the number of subjects where mapping was attempted.

The following hypotheses will be tested:

$$\begin{aligned} H_{03}: q_t &\leq q_c - 0.05 \\ H_{13}: q_t &> q_c - 0.05 \end{aligned}$$

To test this hypothesis we will estimate the difference  $q_t - q_c$  with a 95% two-sided confidence interval. We will perform this analysis using the PP analysis set to test the inferiority hypothesis ( $H_{03}$ ) stated above, and if the lower bound of the interval is greater than -0.05 we will claim non-inferiority. If and only if we reject the inferiority hypothesis ( $H_{03}$ ) we will use the mITT analysis set to test for superiority, and if the lower bound of the interval is greater than 0 we will claim superiority.

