Adenosquamous Carcinoma						
Neuroendocrine						
Clear Cell Carcinoma						
Undifferentiated						
Mixed						
Surgical Procedure						
Hysterectomy						
Radical Hysterectomy						
Radical Trachelectomy						
Bilateral Salpingo-Oophorectomy						
Unilateral Salpingo-Oophorectomy						
Ovarian Transposition						
Sentinel Node Mapping						
Pelvic Node Sampling						
Pelvic Node Dissection						
Para-Aortic Node Sampling						
Para-Aortic Node Dissection						
Other						
Length of Surgery (minutes)						
Median (Min – Max)						
Dose of IC2000 (mg)						
Median (Min – Max)						
Dose of Blue Dye (mg)						
Median (Min – Max)						

Primary Efficacy Outcome

The primary objective of this study is to assess the effectiveness of intraoperative PINPOINT Near Infrared Fluorescence Imaging (PINPOINT) in identification of LNs in subjects with uterine and cervical malignancies who are undergoing LN mapping. Table 3 summarizes the study primary outcome.

Table 3. Lymph Nodes Identified						
Identification Method	B-P Arm		P-B Arm		Total	
	N	%	N	%	N	%
PINPOINT Only						
Confirmed as NOT Lymphatic Tissue						
Confirmed as Lymphatic Tissue						
Confirmed as Lymphatic Tissue (negative for cancer)						
Confirmed as Lymphatic Tissue (positive for cancer)						
Blue Dye Only						
Confirmed as NOT Lymphatic Tissue						
Confirmed as Lymphatic Tissue						
Confirmed as Lymphatic Tissue (negative for cancer)						
Confirmed as Lymphatic Tissue (positive for cancer)						
Both PINPOINT and Blue Dye						
Confirmed as NOT Lymphatic Tissue						
Confirmed as Lymphatic Tissue						
Confirmed as Lymphatic Tissue (negative for cancer)						
Confirmed as Lymphatic Tissue (positive for cancer)						
Following a Fluorescent Duct (No Dye Present in Node)						
Confirmed as NOT Lymphatic Tissue						
Confirmed as Lymphatic Tissue						
Confirmed as Lymphatic Tissue (negative for cancer)						
Confirmed as Lymphatic Tissue (positive for cancer)						
Following a Fluorescent Duct (Blue Dye Present in Node)						
Confirmed as NOT Lymphatic Tissue						
Confirmed as Lymphatic Tissue						
Confirmed as Lymphatic Tissue (negative for cancer)						
Confirmed as Lymphatic Tissue (positive for cancer)						
Following a Blue Duct (No Dye Present in Node)						
Confirmed as NOT Lymphatic Tissue						
Confirmed as Lymphatic Tissue						
Confirmed as Lymphatic Tissue (negative for cancer)						
Confirmed as Lymphatic Tissue (positive for cancer)						

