The first secondary outcome is the ability of PINPOINT and Blue dye to detect at least one lymph node in a subject. Let q_t and q_c represent the proportion of subjects with a least one node identified and confirmed as lymphoid tissue with PINPOINT and Blue dye respectively, divided by the total number of subjects where mapping was attempted. That is, the numerator for q_t is the number of subjects with at least 1 node identified with PINPOINT (PINPOINT alone, both Blue dye and PINPOINT, non-stained node found at termination of Fluorescent duct, Blue-stained node found at termination of a Fluorescent duct, non-stained node found at termination of duct stained with both Blue dye and Fluorescent dye) and confirmed as lymphoid tissue, and the numerator for q_c is the number of subjects with at least 1 node identified with Blue dye (Blue dye alone, both Blue dye and PINPOINT, non-stained node found at termination of Blue duct, Fluorescent-stained node found at termination of Blue duct, non-stained node found at termination of duct stained with both Blue dye and Fluorescent dye) and confirmed as lymphoid tissue. The denominator of both q_t and q_c is the number of subjects where mapping was attempted.

Table 4 summarizes the data to address this secondary objective.

Table 4. Number of Subjects with ≥ 1 Lymph Node Identified						
Identification Method	B-P Arm		P-B Arm		Total	
	N	%	N	%	N	%
PINPOINT						
Blue Dye						
Number of Subjects						

We will test the following hypotheses:

$$H_{03}: q_t \leq q_c - 0.05$$

$$H_{13}: q_t > q_c - 0.05$$

To test this hypothesis we will estimate the difference $q_t - q_c$ with a 95% two-sided confidence interval. We will perform this analysis using the PP analysis set to test the inferiority hypothesis (H_{03}) stated above, and if the lower bound of the interval is > -0.05 we will claim non-inferiority. If and only if we reject the inferiority hypothesis (H_{03}) we will use the mITT analysis set to test for superiority, and if the lower bound of the interval is > 0 we will claim superiority.

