Another secondary outcome is the bilateral LN detection rate. Let b_t and b_c represent the proportion of subjects with at least one node identified on the right side and on the left side of the pelvis and confirmed as lymphoid tissue with PINPOINT and Blue dye, respectively. That is, the numerator for b_t is the number of subjects with at least 1 node identified with PINPOINT (PINPOINT alone, both Blue dye and PINPOINT, non-stained node found at termination of Fluorescent duct, Blue-stained node found at termination of Fluorescent duct, non-stained node found at termination of duct stained with both Blue dye

and Fluorescent dye) on the right side of the pelvis and confirmed as lymphoid tissue and at least 1 node identified with PINPOINT on the left side of the pelvis and confirmed as lymphoid tissue. Similarly, the numerator for b_c is the number of subjects with at least 1 node identified with Blue dye (Blue dye alone, both Blue dye and PINPOINT, non-stained node found at termination of Blue duct, Fluorescent-stained node found at termination of Blue duct, non-stained node found at termination of duct stained with both Blue dye and Fluorescent dye) on the right side of the pelvis and confirmed as lymphoid tissue and at least 1 node identified with Blue dye on the left side of the pelvis and confirmed as lymphoid tissue. The denominator of both b_t and b_c is the number of subjects where mapping was attempted.

Table 5 summarizes the data to address this secondary objective.

Identification Method	B-P Arm		P-B Arm		Total	
	N	%	N	%	N	%
PINPOINT						
Blue Dye						
Number of Subjects						

We will test the following hypotheses:

$$H_{04}: b_t \leq b_c - 0.05$$

$$H_{14}: b_t > b_c - 0.05$$

To test this hypothesis we will estimate the difference $b_t - b_c$ with a 95% two-sided confidence interval. We will perform this analysis using the PP analysis set to test the inferiority hypothesis (H_{04}) stated above, and if the lower bound of the interval is > -0.05 we will claim non-inferiority. If and only if we reject the inferiority hypothesis (H_{04}) we will use the mITT analysis set to test for superiority, and if the lower bound of the interval is > 0 we will claim superiority.

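### The SAP lists for the any-node and bilateral outcomes do not credit a node to the dye that stained it when the node lies on the other dye's duct, which is the reverse of the Protocol's classes

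*SAP*

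**What the plan says.** Call a histologically confirmed node that carries one dye only, but was reached along a duct of the other dye, a cross node.

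**SAP, Secondary Efficacy Outcomes.** The PINPOINT list for q_t includes "Blue-stained node found at termination of a Fluorescent duct", and the list for b_t includes "Blue-stained node found at termination of Fluorescent duct". The Blue dye lists for q_c and b_c contain the run "both Blue dye and PINPOINT, non-stained node found at termination of Blue duct, Fluorescent-stained node found at termination of Blue duct". No list names the cross node that carries its own dye.

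**SAP Table 3.** Cross nodes have their own rows. The row that begins "Following a Fluorescent Duct (Blue Dye Present in Node" stands apart from the Blue-only row, and a mirror row for a fluorescent node on a blue duct stands apart from the PINPOINT-only row. The table's total rows do not say which rows feed which dye.

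**Protocol 8.3.1.3 to 8.3.1.5.** Direct sight of a stained node is the leading criterion for each dye. The duct classes (5 to 7) are for non-stained nodes, so a blue, non-fluorescent node fits class 2 and a fluorescent, non-blue node fits class 1, whatever the duct.

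**Protocol 10.6.** The Blue dye numerator for q counts subjects with "at least 1 node identified with Blue dye (classifications 2, 3, 6, 7) and confirmed as lymphoid tissue"; for PINPOINT the classes are 1, 3, 5 and 7. The class list for b_t is blank in the text available to me, and I take it to be the same as for q_t.

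**The concern.** A visibly blue, confirmed node is what the Protocol means by a Blue dye detection. Under the SAP lists, read with Table 3, that node counts for PINPOINT and not for Blue dye if the surgeon reached it along a fluorescent duct. The same holds in reverse. The two documents therefore score the same node in opposite ways.

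q and b carry formal non-inferiority tests with a 5-point margin, followed by superiority tests, and the SAP says the secondary outcomes are meant to support labelling. Both are yes/no results per subject, so one node can decide a subject's score, above all for b, where a side may have only one or two nodes. If the rule is settled after the data are seen, it becomes a post hoc choice.

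The point is confined to q and b. The primary numerators use a different list, and the duct outcome d is a separate matter.

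**Working it through.** **1. The plan's own figure.** Inputs from Protocol 10.4: "84% and 80% using ICG and Blue dye, respectively", 3.5 nodes per subject, 150 subjects, ICC 0.125, margin 0.05. VIF = 1 + (2 × 3.5 - 1) × 0.125 = 1.75; ESS = 525/1.75 = 300. Power = Φ(0.09/√((0.80 × 0.20 + 0.84 × 0.16)/300) - 1.96) = Φ(2.873 - 1.96) = 0.819, against the stated 82%. It reproduces. It is for the primary endpoint; no power is stated for q or b.

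**2. Credit for one node, as (PINPOINT, Blue).**

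| Cross node | Protocol classes | SAP lists, literal | Both dyes credited |
|---|---|---|---|
| Blue node, fluorescent duct | (0,1) | (1,0) | (1,1) |
| Fluorescent node, blue duct | (1,0) | (0,1) | (1,1) |

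**3. Direction at node level.** Let T and C be the numbers of nodes stained fluorescent and blue, x_B the blue cross nodes and x_F the fluorescent ones. The PINPOINT minus Blue difference in counts is:
- Protocol: T - C
- both credited: (T - C) + (x_B - x_F)
- SAP, literal: (T - C) + 2(x_B - x_F)

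Only the imbalance x_B - x_F matters for the mean. Equal counts cancel.

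**4. Subject arithmetic for b.** Against crediting both, a subject whose Blue bilateral status rests on one cross node goes from (1,1) to (1,0): 1/150 = 0.67 points. Against the Protocol, if both dyes' status rests on that node, it goes from (0,1) to (1,0): 2/150 = 1.33 points. To exceed 5 points takes a net 8 subjects (8/150 = 5.3) or a net 4 (4 × 2/150 = 5.3). If 8% of mappings are aborted, n = 138, and 7 suffice against crediting both (7/138 = 5.1).

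**5. How many nodes that means (assumed model).** One node on a side with probability 0.25, two with 0.75 (mean 3.5 per subject), nodes independent. With node rate p, a side is detected with probability S = 1 - [0.25(1 - p) + 0.75(1 - p)²]; b = S²; q = 1 - (1 - S)².
- At 0.84 and 0.80, b is 0.885 and 0.846.
- If 5% of nodes are blue cross nodes and none fluorescent, the Blue rate falls to 0.75 and b_c to 0.793, a shift of +5.3 points against crediting both. The mirror case gives -4.9. With 5% each way the net is 0.4.
- A 5-point shift needs 4.7% of nodes one way (about 25 of 525). With node rates calibrated to the published bilateral rates of 65% and 43% (Protocol 1.1.4), it needs 3.7% (about 19). Against the Protocol rule the figures are 2.5% and 1.9%.
- For q at the planned rates, 5% of nodes one way shifts the difference by 0.6 points, and 5 points needs about 22% of nodes. At the 65%/43% calibration, 6.1% would do it.

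**6. Precision.** Balanced cross nodes still turn (1,1) subjects into discordant ones relative to crediting both. In a simulation at 0.84 v 0.80 (1 + Poisson(0.75) nodes per side, probit-normal side effect with latent ICC 0.3, between-method correlation 0.2), a quarter of the single-stained nodes in each direction were made cross nodes, or 3.1% and 4.1% of all nodes. Discordance on b was 22.6% with both credited and 29.3% under the SAP lists. Ignoring the squared difference, the 95% half-width goes from 1.96√(0.226/150) = 7.6 points to 1.96√(0.293/150) = 8.7 points. Power for non-inferiority on b fell from about 60% to about 40%. Part of that fall is a mean shift of about 1 point, because the two counts were not equal. These values move by a few points with how the correlation is modelled.

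**The case against.** The strongest reply is that the literal reading is not the intended one. The SAP's list of nodes found by any method has seven categories and no cross category. If that list is exhaustive, cross nodes must sit in the single-dye entries, and then q and b already credit both dyes: one through the stain, the other through the duct entry. Table 3 is only an empty mock-up. This reading is possible. But the SAP does not state it, Table 3 points the other way, and it leads to the same list wording as the fix below.

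Three stronger inferences are tempting, and the documents do not support them.
- *That the lists favour PINPOINT.* They are symmetric; the net effect can go either way.
- *That b_t - b_c will shift by more than the margin.* No cross-node frequency is given. One simulated setting (node rates 0.72 v 0.80, half of blue-only and a quarter of fluorescent-only nodes lying on the other dye's duct) raises non-inferiority claims on b from about 21% with both credited to about 77%. It needs about 13% of all nodes to be cross nodes, skewed some 3 to 1, at rates that reverse the planned ordering.
- *That equally frequent cross nodes shrink and then reverse the contrast.* The factor (1 - 2r) arises only if the same fraction r of two unequal groups is affected. Equal counts leave the mean nearly unchanged (step 3).

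It is also fair to say that the loss of precision is relative to crediting both dyes. The Protocol rule makes these subjects discordant too.

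**Conclusion.** The inconsistency is real. As written, the SAP withholds credit from the dye that stained the node, and the Protocol gives credit to that dye alone. Nothing in the SAP states the softer reading.

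The size is conditional. It rests on how often each kind of cross node occurs and how unequal the two are, and neither is in the documents. A net 8 of 150 subjects in one direction, against crediting both dyes, would move b by more than its margin; against the Protocol rule, 4 would. Balanced counts would cost precision rather than bias the estimate. At the planned rates q is hardly affected, though at lower detection rates it would be less robust. Only secondary outcomes are involved, but they are tested formally and meant for labelling, so the rule should be settled before analysis.

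**What to change.** In the SAP, credit a stained node to its own dye for q and b. Add the entry "Blue-stained node found at termination of a Fluorescent duct" to the q_c and b_c lists, and add the mirror entry (fluorescent-stained node at the end of a blue duct) to q_t and b_t. A cross node then counts for both dyes. State for every Table 3 row which dye or dyes it counts for in Tables 4 and 5. Report q and b under the Protocol classes (1, 3, 5, 7 for PINPOINT; 2, 3, 6, 7 for Blue dye) as a sensitivity analysis.

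The cost is a few list entries and one added run. Crediting both dyes is more generous to the duct dye than the Protocol classes are; the sensitivity analysis shows by how much. No new CRF field is needed if node stain and duct stain are already recorded separately, as the Table 3 rows imply. No extra subjects or procedures are involved.

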STATISTICAL ANALYSIS PLAN

FILM Study:

**A Randomized, Prospective, Open Label, Multicenter Study Assessing the Safety and Utility of PINPOINT®
Near Infrared Fluorescence Imaging in the Identification of Lymph Nodes in Subjects with Uterine and
Cervical Malignancies who are Undergoing Lymph Node Mapping**

Sponsor:

Novadaq Technologies Inc.

Prepared by:

[name]

Senior Research Statistician
MD Anderson Cancer Center

June 23, 2017

Introduction

The FILM study compares lymph node (LN) detection with IC2000 to node detection with isosulfan blue. In the study, approximately 150 evaluable subjects with clinical stage 1 endometrial cancer or clinical stage 1A cervical cancer who are scheduled to undergo minimally invasive surgery with lymphatic mapping are randomized to one of two groups (arms):

- P-B arm: subjects will have IC2000 injected into the cervix initially followed by isosulfan blue cervical injection; subsequent LN mapping will be performed first for IC2000 mapping followed by isosulfan blue mapping, or
- B-P arm: subjects will have isosulfan blue injected into the cervix initially followed by IC2000 cervical injection; subsequent LN mapping will be performed first for isosulfan blue mapping followed by IC2000 mapping.

Mapping is only considered complete when all nodes meeting the criteria outlined in the protocol (all nodes identified and mapped by isosulfan blue or IC2000 or both and all visibly or palpably abnormal nodes) are documented and the surgeon has performed a full 360-degree scan of the area within the abdominal cavity. Further, fluorescent ducts are to be followed in both directions in order to identify LNs to be excised. Surgeons will then excise all mapped LNs. It is also important to note that, in addition to mapping of LNs in accordance with the guidelines from the NCCN for Uterine Neoplasms, SLN Algorithm for Surgical staging of Endometrial Cancer or the NCCN guidelines for Cervical Neoplasms, Surgical/SLN Mapping Algorithm for Early-stage Cervical Cancer, the site investigators are to remove additional LNs according to their standard of care for the patient (refer to page 37 of the FILM protocol), a consideration that is personalized based upon surgical experience, intra-operative observations, patient co-morbidities and other factors.

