Following a Blue Duct (Fluorescent Dye Present in Node)						
Confirmed as NOT Lymphatic Tissue						
Confirmed as Lymphatic Tissue						
Confirmed as Lymphatic Tissue (negative for cancer)						
Confirmed as Lymphatic Tissue (positive for cancer)						
Following a Blue and Fluorescent Duct (No Dye Present in Node)						
Confirmed as NOT Lymphatic Tissue						
Confirmed as Lymphatic Tissue						
Confirmed as Lymphatic Tissue (negative for cancer)						
Confirmed as Lymphatic Tissue (positive for cancer)						

Table 3. Lymph Nodes Identified

Identification Method	B-P Arm		P-B Arm		Total	
	N	%	N	%	N	%
Appearance (No Dye Present in Node)						
Confirmed as NOT Lymphatic Tissue						
Confirmed as Lymphatic Tissue						
Confirmed as Lymphatic Tissue (negative for cancer)						
Confirmed as Lymphatic Tissue (positive for cancer)						
Total						
PINPOINT						
Confirmed as NOT Lymphatic Tissue						
Confirmed as Lymphatic Tissue						
Blue Dye						
Confirmed as NOT Lymphatic Tissue						
Confirmed as Lymphatic Tissue						
Neither Dye						
Confirmed as NOT Lymphatic Tissue						
Confirmed as Lymphatic Tissue						
Total						

To assess the effectiveness of PINPOINT in the identification of LNs, a non-inferiority test will be performed using the per-protocol (PP) analysis set.

$$H_{01}: p_t \leq p_c - 0.05$$

$$H_{11}: p_t > p_c - 0.05$$

Here p_t and p_c represent the effectiveness of LN mapping with PINPOINT and Blue dye respectively. We define the numerator for p_t as the number of nodes identified with PINPOINT (i.e., with PINPOINT alone or with both Blue dye and PINPOINT) and confirmed as lymphoid tissue, and we define the numerator for p_c as the number of nodes identified with Blue dye (i.e., with Blue dye alone or with both Blue dye and PINPOINT) and confirmed as lymphoid tissue. We define the denominator for both p_t and p_c as the number of nodes identified by ANY method (i.e., PINPOINT alone, Blue dye alone, both Blue dye and PINPOINT, abnormal appearance or palpably hard, non-stained node found at termination of Fluorescent duct, non-stained node found at termination of Blue duct, non-stained node found at termination of duct stained with both Blue dye and Fluorescent dye). The denominator will include excised nodes confirmed as lymphoid tissue.

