A third secondary outcome is the proportion of LNs identified by following lymphatic channels (ducts). Let d_t and d_c represent the proportion of nodes identified by following a duct and confirmed as lymphoid tissue with PINPOINT and Blue dye, respectively. That is, the numerator for d_t is the number of nodes identified with PINPOINT by following a duct (non-stained node found at termination of Fluorescent duct, Blue-stained node found at termination of a Fluorescent duct, non-stained node found at termination of duct stained with both Blue dye and Fluorescent dye) and confirmed as lymphoid tissue. Similarly, the numerator for d_c is the number of nodes identified with Blue dye by following a duct (non-stained node found at termination of Blue duct, Fluorescent-stained node found at termination of a Blue duct, non-stained node found at termination of duct stained with both Blue dye and Fluorescent dye) and confirmed as lymphoid tissue. We define the denominator for both d_t and d_c as the number of nodes identified by ANY method. The denominator will include excised nodes confirmed as lymphoid tissue.

Table 6 summarizes the data to address this secondary objective.

Table 6. Number of Subjects with Lymph Nodes Identified by Following a Duct

Identification Method	B-P Arm		P-B Arm		Total	
	N	%	N	%	N	%
PINPOINT						
Blue Dye						
Number of Subjects						

We will test the following hypotheses:

$$H_{05}: d_t \leq d_c - 0.05$$

$$H_{15}: d_t > d_c - 0.05$$

To test this hypothesis we will estimate the difference $d_t - d_c$ with a 95% two-sided confidence interval. We will estimate this confidence interval in a manner similar to that described for the primary outcome. We will perform this analysis using the PP analysis set to test the inferiority hypothesis (H_{05}) stated above, and if the lower bound of the interval is > -0.05 we will claim non-inferiority. If and only if we reject the inferiority hypothesis (H_{05}) we will use the mITT analysis set to test for superiority, and if the lower bound of the interval is > 0 we will claim superiority.

We will also estimate overall percent agreement, positive percent agreement, and negative percent agreement with exact (Clopper-Pearson) 95% confidence intervals. The data will be summarized as shown in Table 7.

Table 7. Agreement of PINPOINT with Blue Dye

		Blue Dye (Reference)		Total
		(+)	(-)	
PINPOINT (Test)	(+)	A	B	A + B
	(-)	C	D	C + D
Total		A + C	B + D	

We define the following quantities:

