- overall percent agreement = $100\% \times (A + D) / (A + B + C + D)$
- positive percent agreement = $100\% \times A / (A + C)$
- negative percent agreement = $100\% \times D / (B + D)$

As sensitivity analyses, we will perform the non-inferiority tests of these secondary outcomes using the mITT analysis set. We will also perform sensitivity analyses of these secondary endpoints using a best-case and a worst-case scenario. The best-case scenario will consider nodes with missing histology to be lymphoid tissue for PINPOINT and non-lymphoid tissue for Blue dye. The worst case scenario will consider nodes with missing histology to be non-lymphoid tissue for PINPOINT and lymphoid tissue for Blue dye.

The last secondary objective of the study is to find the anatomic distribution of lymph nodes. Table 8 summarizes the data to address this secondary objective. We will use Fisher's exact test to compare study arms with respect to the distribution of anatomic location of lymph nodes for each identification method. We will also use Fisher's exact test to compare identification methods with respect to the distribution of anatomic location of lymph nodes. We summarize these data using both the PP and mITT analysis sets.

Identification Method	B-P Arm		P-B Arm		Total	
	N	%	N	%	N	%
PINPOINT						
Left obturator/internal iliac						
Left external iliac						
Left common iliac						
Right obturator/internal iliac						
Right external iliac						
Right common iliac						
Presacral						
Para-aortic node below IMA						
Para-aortic node above IMA						
Other						
Blue Dye						
Left obturator/internal iliac						
Left external iliac						
Left common iliac						
Right obturator/internal iliac						
Right external iliac						
Right common iliac						
Presacral						
Para-aortic node below IMA						
Para-aortic node above IMA						
Other						
Following a Channel (No Dye Present in Node)						
Left obturator/internal iliac						
Left external iliac						
Left common iliac						
Right obturator/internal iliac						
Right external iliac						
Right common iliac						
Presacral						
Para-aortic node below IMA						
Para-aortic node above IMA						
Other						
Appearance (No Dye Present in Node)						
Left obturator/internal iliac						
Left external iliac						
Left common iliac						
Right obturator/internal iliac						
Right external iliac						
Right common iliac						
Presacral						
Para-aortic node below IMA						
Para-aortic node above IMA						
Other						

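### SAP Table 7 does not state its unit; if it counts nodes, the exact binomial intervals ignore clustering and are modestly too narrow, and negative agreement depends on which undyed nodes are recorded

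*SAP*

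**What the plan says.** After the duct outcome, the SAP adds three agreement measures: "We will also estimate overall percent agreement, positive percent agreement, and negative percent agreement with exact (Clopper-Pearson) 95% confidence intervals". The layout is headed "Table 7. Agreement of PINPOINT with Blue Dye", with Blue dye as reference and cells A to D. Overall agreement is (A+D)/(A+B+C+D), positive agreement A/(A+C), and negative agreement D/(B+D). The cells carry no unit, (+) and (-) are not defined, and neither the eligible nodes nor the analysis set is named.

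The neighbouring outcomes are mixed:

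- **Duct outcome, immediately before:** node level. "We define the denominator for both d_t and d_c as the number of nodes identified by ANY method".
- **At-least-one-node outcome:** subject level. "The denominator of both q_t and q_c is the number of subjects where mapping was attempted". Bilateral detection has the same denominator.

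Elsewhere nodes are treated as clustered. Protocol section 10.4 states: "The power calculation was performed for a 2-level hierarchical model in which nodes are nested within subject". The SAP's primary interval uses the Nam-Kwon method for clustered matched pairs, and the duct outcome is to follow a similar approach.

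Undyed nodes can reach the node data. The primary denominator includes nodes of "abnormal appearance or palpably hard", and the SAP introduction says that "the site investigators are to remove additional LNs according to their standard of care for the patient".

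**The concern.** A Clopper-Pearson interval assumes independent observations. Nodes from one patient share the injection, the surgeon and the lymphatic anatomy, and the plan itself assumes that they are correlated. If Table 7 counts nodes, its intervals are at odds with the methods for the primary and duct outcomes and claim more precision than the data carry.

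The second issue is the double-negative cell, D. A node that neither method finds enters the data only if something else causes it to be recorded, such as abnormal appearance or, possibly, standard-of-care removal. Negative agreement then depends partly on what surgeons choose to take out. Because Blue dye is labelled as the reference, a reader may treat the figure as a specificity.

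What is at stake is how a set of descriptive statistics is read. They sit among secondary outcomes meant to support labelling, but have no hypothesis, margin or success rule of their own.

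**Working it through.** **Inputs (Protocol 10.4):** 150 subjects, 3.5 nodes per subject, 525 nodes; ICC estimated at 0.07 and at most 0.125; detection 84% (ICG) and 80% (Blue dye); margin 5%; power at least 82% at an effective sample size of 300. The documents give no expected agreement, no ICC for agreement and no expected size for cell D.

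**1. The plan's own figure.** VIF = 1 + (2 × 3.5 − 1) × 0.125 = 1.75, and 525/1.75 = 300. SE = √[(0.84×0.16 + 0.80×0.20)/300] = 0.0313. Power = Φ(0.09/0.0313 − 1.96) = 81.9%. The stated 82% reproduces.

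**2. A node-level Table 7 at the design rates.** If the two methods were independent (an assumption), A = 352.8, B = 88.2, C = 67.2 and D = 16.8. Overall agreement is then 70.4% of 525, positive agreement 84% of 420, and negative agreement 16% of 105.

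**3. Interval width.** Each node gives one agree-or-disagree result, so VIF = 1 + (m − 1) × ICC. Here m = 3.5 for overall agreement and 420/150 = 2.8 for positive agreement. The adjusted interval is Clopper-Pearson on n/VIF.

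| Statistic | ICC | VIF | Unadjusted 95% | Adjusted 95% | √VIF | Width ratio |
|---|---|---|---|---|---|---|
| Overall | 0.07 | 1.175 | 66.3–74.3% | 65.9–74.6% | 1.084 | 1.086 |
| Overall | 0.125 | 1.3125 | 66.3–74.3% | 65.7–74.8% | 1.146 | 1.149 |
| Positive | 0.07 | 1.126 | 80.1–87.4% | 79.9–87.6% | 1.061 | 1.063 |
| Positive | 0.125 | 1.225 | 80.1–87.4% | 79.7–87.7% | 1.107 | 1.110 |

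The protocol's VIF of 1.75 would make the overall interval 33% wider (64.9–75.5%). That VIF counts two readings per node, whereas an agreement result is one per node, so I do not rely on it.

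**4. Coverage.** The approximation 2Φ(1.96/√VIF) − 1 gives 92.9% and 91.3% for overall agreement, and 93.5% and 92.3% for positive agreement, at ICC 0.07 and 0.125. I also ran a beta-binomial simulation with 150 subjects, 8,000 replicates, true proportions 0.704 and 0.84, and cluster sizes of 3–4 or Poisson with mean 3.5. The unadjusted interval covered 92.0–93.5% at ICC 0.07 and 91.0–92.1% at ICC 0.125. With ICC near zero it covered at least 95%, as it should.

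**5. Negative agreement.** With both detection rates held at the design values, 105 nodes are blue-negative and 84 are PINPOINT-negative, so D can be anything from 0 to 84.

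| D (nodes) | Overall | Positive | Negative, D/105 |
|---|---|---|---|
| 0 | 64% | 80% | 0% |
| 16.8 (independence) | 70.4% | 84% | 16% |
| 42 | 80% | 90% | 40% |
| 84 | 96% | 100% | 80% |

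Selection acts directly. If k further undyed nodes were eligible, A, B and C would not change, but negative agreement would become (D + k)/(B + D + k). Starting from independence and taking k = 50 (an assumption), it moves from 16% to 66.8/155 = 43% with no change in what either dye found. Overall agreement also moves; positive agreement, A/(A+C), does not.

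The average-cluster VIF does not suit negative agreement. There are only 105/150 = 0.7 blue-negative nodes per subject, and failed mapping may concentrate them in a few subjects, so no widening is quoted for it.

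**The case against.** The strongest reply is that the SAP never says Table 7 counts nodes. Tables 4 to 6 each end in a row for subjects, and two of the three preceding outcomes are at subject level. If Table 7 counts subjects, the observations are independent and Clopper-Pearson is valid. This stands, and it makes the interval point conditional.

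A reader might go further and infer that negative agreement is near zero by construction and therefore uninterpretable. The documents do not support that:

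- The design rates allow 0 to 80%.
- Abnormal nodes fill cell D, and standard-of-care nodes might. Read literally, the SAP's primary numerators cover only nodes found with one dye or both, so undyed duct-found nodes would fall there too. The protocol's numerators (section 10.2) count those nodes as found.
- If (+) means found by following a duct, as in the outcome just before the table, ordinarily stained nodes fall in D and negative agreement is high: 90 to 98% if 2 to 10% of nodes are duct-found by each method independently (assumed shares).

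Nor do the documents show that a subject-level table would be forced toward zero because double failures drop out of the per-protocol set. Table 7 is not assigned to that set, and the subject-level outcomes already use all subjects in whom mapping was attempted.

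Materiality is also limited. The widening is modest, the ICC of 0.125 is the protocol's ceiling, and SAP Table 3 already has a row for nodes found with neither dye. That limits the weight of the point, but the choice still has to be made before analysis, because the readings give very different values.

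**Conclusion.** The point holds conditionally and is modest in size. Table 7 is under-specified. On the node-level reading suggested by its position, the prescribed intervals are too narrow: by about 8 to 15% for overall agreement and 6 to 11% for positive agreement, with true coverage about 91 to 94% instead of 95%. This assumes that the protocol's ICC of 0.07 to 0.125, given for its detection power calculation, carries over to agreement, and that the methods agree about as often as independence would give. On a subject-level reading there is no interval problem.

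Node-level negative agreement is undefined until the eligible nodes are stated, and it then depends on selection. It is not fixed near zero, but it should not be read as a specificity.

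The statistics are descriptive. The primary non-inferiority test, its clustered variance and its power are unaffected.

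**What to change.** Amend the SAP text around Table 7 to:

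1. State the unit, the meaning of (+) and (-) including how duct-found nodes are classed, the eligible nodes (in particular whether undyed standard-of-care nodes count), and the analysis set.
2. For any node-level agreement statistic, replace Clopper-Pearson with a subject-level bootstrap or a cluster-robust interval, in line with the primary and duct outcomes.
3. Keep Clopper-Pearson only for a subject-level table among subjects in whom mapping was attempted.
4. Next to any node-level negative agreement, report the count and source of cell D (abnormal appearance, undyed duct-found, standard of care), and note that the figure is not a specificity.

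This changes SAP wording only and needs no new data. The cost is slightly wider intervals and a little more analysis work.
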